3.9 Cost and cost effectiveness

Evaluation of cost and cost-effectiveness of the optimized implementation model is essential to provide the economic evidence required by policymakers to adopt the model. Specifically:

 Affordability: Estimates of the total additional annual cost of including the model into the country level health systems, including cost per child to receive intervention in the M-SNCU, societal cost, provider, and beneficiary cost.

- **Cost-effectiveness**: The cost-effectiveness of the iKMC intervention will be compared in a selected cluster between the control and intervention period.
- **Sensitivity analysis**: Identification of key cost and epidemiological inputs that have the greatest influence on total cost and cost-effectiveness.

Costs will firstly be categorized as: research-related, programmatic, or shared research/programme costs. We will use programmatic costs only wherever possible. Programmatic cost of start-up and recurrent cost will be collected throughout the stepped-wedge trial phase: (i) preparation phase, such as establishing necessary infrastructure; and (ii) implementation phase, such as capital and recurrent costs including initial training costs and refresher training costs, running costs, salaries, procurement and maintenance costs, other training costs, quality assurance procedures, installation of equipment; and monitoring including technical support, IT equipment and resolving unexpected obstacles, cost of institutionalization; incremental costs for incorporating in HMIS, establishing dash board and periodic review meetings with all stakeholders. The exact items to be costed will depend on the final composition of the optimized implementation model and will be identified in consultation with local stakeholders and health economics experts. We will use standard methods in consultation with health economics experts including the WHO CHOICE tool.⁴⁸

3.10 Laying the foundation for a platform that enables introduction of additional MNH and small and sick Newborn interventions

The focus of this implementation research study is iKMC, however, the platform created can be used to introduce other small and sick newborn interventions, and other maternal and newborn health interventions. The study will build capacity of local research teams and programme implementers to conduct large-scale implementation research and will demonstrate the value of the research to a wider audience. We anticipate that the increased understanding, uptake, and 'institutionalization' of implementation science in health programmes in the participating country health system will result in important benefits.

4. Recruitment of participants, study data collection and management 4.1 Recruitment of participants

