2.2 Secondary objectives

- 1. To ascertain the costs and cost effectiveness of immediate KMC implemented at scale
- 2. To lay the foundation for research implementation platforms that can assess other maternal and newborn health (MNH) interventions and care for preterm or LBW babies.

3. Methods

[figure not shown]

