The stepped-wedge design is a unidirectional crossover design where all clusters start in the control phase (i.e., minimum package of care for small and sick newborns) and cross over to the intervention (i.e., the optimized iKMC implementation model) at different timepoints, till all clusters have transitioned to the intervention condition. All 3 clusters in the state will start with the control condition (see Figure 10). At each equally spaced cross-over time, one cluster will transition to the immediate KMC implementation model based on a pre-allocated random sequence. A three-month transition period is included in each cluster to allow for the implementation model to be operationalized. All the implementation strategies which are part of the optimized model will be implemented during this period. Briefly, these will include infrastructural changes (e.g., M-SNCUs), supplies (e.g. KMC beds, chairs, and garments), staff training and supervision, monitoring and feedback in the immediate KMC implementing facilities, and strengthening of newborn care to ensure early identification and referral of eligible infants to the immediate KMC implementing facility in skin-to-skin contact with the mother or surrogate, and strengthening of referral pathways. Once each cluster has crossed to the intervention, it will continue to be exposed to it for the remaining duration of the study. The coverage outcomes will be analyzed at the state and country level (along with another similarly designed study to be conducted in Haryana). However, impact outcomes, i.e., pre-discharge and neonatal mortality will be pooled and analyzed at the country level (along with another similarly designed study to be conducted in Haryana) and ascertained at a global level in combination with data from multiple countries by the WHO.

The rationale for a stepped-wedge design in evaluating the effectiveness of the optimized implementation model is as follows:

- There are clear benefits to the use of iKMC for newborns. Therefore, it is important for the governments/ ministries /policymakers and the local healthcare providers involved in this implementation research study to be assured that no districts/patients are denied improved access to iKMC because of being part of a research project. Through this design, they can participate in a randomized trial and all clusters can be guaranteed to receive the intervention.

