- The optimized iKMC implementation model is a complex service delivery intervention. The step wedge design takes advantage of the logistical needs of delivering a complex service delivery intervention, by rolling this out in a staggered fashion to all participating sites.
- The design ensures a randomized comparison group is available to generate high-quality evidence when time trends are taken into account.

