3.7.7. Statistical analysis of the stepped-wedge trial

Sample size and power calculations

The coverage outcomes from the trial will be assessed at the state and country level (to be pooled with data from a similar study in Haryana). The impact outcomes – pre-discharge mortality and NMR, will be pooled at a country level along with Haryana, and ascertained at a global level in combination with data from other countries by the WHO for adequate statistical power.

Due to the paucity of reliable preterm birth data, sample size calculations are based on LBW estimates. The sample size for clusters has been estimated at WHO based on the average characteristics across sites, and is not UP or India-specific. We estimated that an average of 500 LBW newborns (<2 kg) born in a cluster in an iKMC implementing facility(ies) or transferred to the hospital(s) before 24hr from birth per year will be required to ensure adequate sample size. This was calculated based on birth rate of 2%, resulting in estimated 20,000 livebirths. Of which, we assumed that yearly 5% of LBW newborns would require care at SNCU (1000 LBW infants a year). We then assumed that 60% of LBW newborns requiring care at SNCU would be inborn babies or transferred to SNCU within 24 hours after birth (approximately 600 LBW newborns). To allow for varying cluster sizes within country/districts, we have assumed a 0.75 variation coefficient.

Parameter	Estimates
No. of LBW newborns requiring care in level-2 units	500/year (125/quarter)
born in facilities or transferred to facility within 24 hours	
after birth in one district	
Neonatal mortality before discharge in control periods	15%
(based on the WHO immediate KMC trial) [‡]	
Relative mortality reduction	20%
Intra-cluster correlation	0.01 (0.005 to 0.02)
Cluster auto-correlation coefficient	90%
Coefficient of variation of cluster size	0.75

Statistical power calculations consider both the clustered and stepped-wedge nature of the design. To allow for clustering, it is necessary to have estimates of intra-cluster correlations (ICC). We have been guided by patterns and determinants of ICCs as per WHO Global Survey estimations.²² For mortality outcome we have assumed an ICCs of 0.01 (considered sensitivity at 0.005 to 0.02). Considering the

[‡] WHO Immediate KMC Study Group, Arya S, Naburi H, Kawaza K, et al. Immediate "Kangaroo Mother Care" and Survival of Infants with Low Birth Weight. N Engl J Med. 2021 May 27;384(21):2028-2038.

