Outcome (rates, proportions, mean/median, as appropriate) will be compared by exposure status (intervention and control). For the primary and secondary outcomes, a multilevel logistic regression model will be used to estimate the effect of the intervention. The binomial distribution and log link function will be considered. The relative risk and the 95% confidence interval will be reported as the effect size estimate. The statistical analysis will adjust for clustering in the data, calendar time, and varying treatment effect between clusters, countries, and with time. We will also consider including the length of the intervention period in the model as an effect modifier. All analyses will be carried out using STATA 14.1. The main analysis will be carried out once all outcome data have been entered into the study database and validated as being ready for analysis. A comprehensive statistical analysis plan will be developed in discussion with the trial statistician. The statistical analysis plan will be written, approved, and finalized prior to the commencement of trial recruitment.

3.8 Promote and support the government to scale up iKMC at provincial and national level

The overarching aim of this project is not only to develop optimized models for iKMC, but to make these models available for scale up nationally and internationally to reduce newborn morbidity and mortality. The project will have established both the necessary evidence base for scaling up iKMC, as well as the necessary resources, tools, materials, and strategies to do so. Assuming effectiveness, this will become the established international standard by which iKMC can be adopted and optimized across all settings. We would also have addressed questions of scalability related to scale up approach, capacity, and investment. Above all, the government would already have had the experience of implementing iKMC in multiple districts as well as observed its benefits.

Accordingly, a scale-up strategy will be develop in close consultation with the state and national government with the research team providing the necessary technical support. This is in alignment with the ongoing scale-up of KMC in UP. Findings from the study will be consolidated by the WHO with findings from other countries to propose a global model for scaling up immediate KMC. WHO will also involve the STAGE-MNCAH&N-KMC Working Group, which is a multi-partner group in these efforts.

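### Cost-effectiveness is set as a before-after comparison within one selected cluster, which uses no randomisation and cannot separate iKMC from a secular trend

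*Protocol*

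**What the plan says.** Protocol section 3.9 fixes the comparison: "The cost-effectiveness of the iKMC intervention will be compared in a selected cluster between the control and intervention period". It gives no rule for choosing the cluster, no concurrent control and no adjustment for time. The comparison serves the first secondary objective in section 2.2: "To ascertain the costs and cost effectiveness of immediate KMC implemented at scale".

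Section 3.7.2 describes a one-way crossover: "The stepped-wedge design is a unidirectional crossover design where all clusters start in the control phase". What is randomised is the order in which clusters cross: "At each equally spaced cross-over time, one cluster will transition to the immediate KMC implementation model based on a pre-allocated random sequence". The same section states the condition under which the design works: "The design ensures a randomized comparison group is available to generate high-quality evidence when time trends are taken into account".

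Section 3.7.7 follows that condition for the effect analyses. "For the primary and secondary outcomes, a multilevel logistic regression model will be used to estimate the effect of the intervention", and "The statistical analysis will adjust for clustering in the data, calendar time, and varying treatment effect between clusters, countries, and with time". Mortality is pooled by country and then "ascertained at a global level in combination with data from other countries by the WHO for adequate statistical power". Cost-effectiveness is not named in that model, and section 3.9 does not refer to it.

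**The concern.** Within one cluster the control quarters always come first. A contrast between its two periods therefore measures the intervention plus whatever else changed over time in that district. The comparison between clusters that cross at different times, which is what the randomisation provides, is not used.

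At stake is the evidence that section 3.9 itself says policymakers need in order to adopt the model. If the effectiveness term comes from one cluster, the cost per death averted carries any secular trend as bias. Its denominator would also be too imprecise to exclude zero, so the interval for the ratio would be unbounded. The data for a better estimate are already being collected.

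**Working it through.** **Inputs.** From section 3.7.7: 125 infants per cluster per quarter; 15% control and 12% intervention mortality (3 points); intra-cluster correlation (ICC) 0.01; cluster autocorrelation 0.90; coefficient of variation of cluster size 0.75; 24 clusters; 92% power at 5%, taken as two-sided. From Figure 10: the three sequences have 1, 3 or 5 control quarters, one unmeasured transition quarter, and 6, 4 or 2 intervention quarters.

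**1. The plan's own figure.** Power = Φ(0.03/SE − 1.96). The SE comes from generalised least squares on cluster-period means, with fixed period effects and random cluster and cluster-by-period effects. With eight clusters per sequence this gives 91.6% if the transition quarters count as measured, which reproduces the stated 92%.
- The SE implied by 92% power is 0.03/(1.96 + 1.405) = 0.0089, about 0.9 points. The 95% interval around 3 points is 1.3 to 4.7.
- With transition quarters excluded, power is about 80% and the SE is 0.03/(1.96 + 0.84) = 0.0107, about 1.1 points. The interval is 0.9 to 5.1.

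**2. Can one cluster give a time-adjusted effect?** No. One cluster has 7 measured quarters. Seven period effects plus one treatment effect make 8 parameters, but the treatment column is the sum of the intervention-quarter columns. The design matrix has rank 7 in all three sequences.

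**3. Precision of the unadjusted contrast.** The cluster effect cancels within a cluster and the cluster-by-period part remains: 0.01 × (1 − 0.90) × 0.11655 = 0.000117, where 0.11655 is the mean of 0.15 × 0.85 = 0.1275 and 0.12 × 0.88 = 0.1056. With n infants and q quarters in the control (c) and intervention (i) periods:

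Variance = 0.1275/n_c + 0.1056/n_i + 0.000117 × (1/q_c + 1/q_i)

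| Sequence | n_c vs n_i | Variance | SE (points) | 95% interval around 3 points |
|---|---|---|---|---|
| 1 | 125 vs 750 | 0.001020 + 0.000141 + 0.000137 = 0.00130 | 3.6 | −4.1 to 10.1 |
| 2 | 375 vs 500 | 0.000340 + 0.000211 + 0.000068 = 0.00062 | 2.5 | −1.9 to 7.9 |
| 3 | 625 vs 250 | 0.000204 + 0.000422 + 0.000082 = 0.00071 | 2.7 | −2.2 to 8.2 |

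The same power formula gives about 13%, 23% and 20%. If the between-period correlation decays with time, the single-cluster SEs rise to 4.2, 3.4 and 3.6 points. The pooled SE without transition quarters rises to about 1.2 (power about 70%: 0.03/(1.96 + 0.52)).

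A larger cluster helps only slowly. In sequence 2, the most favourable, zero is excluded only if the variance is below (0.03/1.96)² = 0.000234. The sampling part, 0.000551, must then fall to 0.000234 − 0.000068 = 0.000166, which needs a cluster about 3.3 times the average size.

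**4. Secular trend.** Mean midpoints, in quarters from the start, are 0.5 and 5.0 (sequence 1), 1.5 and 6.0 (sequence 2), and 2.5 and 7.0 (sequence 3). The gap is always 4.5 quarters, or 1.125 years. The protocol gives no trend in mortality. For an assumed fall of 0.5 to 1.5 points per year from other causes, the bias is 0.5 × 1.125 = 0.56 to 1.5 × 1.125 = 1.69 points, which is 19% to 56% of the planned effect.

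**5. Season.** Each sequence has at least one calendar quarter under both conditions: Q1 in sequence 1; Q1 to Q3 in sequence 2; Q3 and Q4 in sequence 3. Season is therefore unbalanced but could be matched, with fewer infants and still a year or more between the matched quarters.

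**The case against.** The strongest reply is that section 3.9 never names the source of the effectiveness term. It mentions epidemiological inputs in the sensitivity analysis, and it defers to standard methods, health economics experts and the WHO CHOICE tool. The sentence may have been meant only to place cost collection in one district, and an economic plan that is not shown may say more. A reader might infer that the investigators have decided against using the pooled randomised effect. The protocol does not support that: nothing in it excludes the pooled estimate as an input. What stands is narrower. The sentence says that cost-effectiveness, not cost, is compared between periods in that cluster, and no analysis plan can add calendar-time adjustment to a single-cluster contrast.

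Other stronger readings also fail:
- **Full confounding with season.** Figure 10 shows overlapping calendar quarters in every sequence.
- **A cluster chosen to favour the result.** The protocol gives no selection rule, so the method is unstated, not shown to be biased.
- **Care certain to be still improving during the trial.** Section 3.7.1 says strengthening ends before the evaluation starts, while the legend of Figure 10 describes it as part of the control period. A trend is plausible, but its size is unknown.

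It is also fair to say that a four-country effect combined with one Indian district's costs needs its own assumption, since section 3.7.7 expects the effect to vary between clusters and countries. That objection stands, and the fix has to address it.

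**Conclusion.** The point holds on the plain reading of section 3.9. The comparison it fixes is unrandomised, cannot be adjusted for calendar time, and departs from the conditions that sections 3.7.2 and 3.7.7 set for the trial's effect estimates. Its SE is roughly two to four times the pooled one. The precision figures assume a cluster of average size and the protocol's ICC and autocorrelation. The bias range rests on an assumed trend.

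The point concerns a secondary objective. The primary mortality analysis and safety monitoring are untouched. It should be corrected before the economic analysis is fixed, but it does not threaten the trial.

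**What to change.** Amend section 3.9 to say that:
- incremental deaths averted come from the pooled, calendar-time-adjusted stepped-wedge model, with its uncertainty carried into the cost-effectiveness result (the reported relative risk is converted to a risk difference at a stated control risk);
- the selected cluster or clusters supply unit costs and resource use, with the method of choosing them stated;
- any mortality contrast within a single cluster is descriptive;
- a sensitivity analysis uses the country-level pooled estimate.

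The last item addresses the main downside, which is the assumption that the pooled effect applies to the costed setting. It will be imprecise. With 6 clusters in place of 24, the SE roughly doubles (√(24/6) = 2) to about 1.8 to 2.2 points, so its interval around 3 points would also include zero (1.96 × 1.8 = 3.5). It does, however, remain randomised and time-adjusted.

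The cost is a short wording change in section 3.9. No new trial data are needed, because section 3.7.2 already plans both the country-level and the global mortality analyses. Costing in more than one cluster would be extra work and is optional.

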4.1.1 For the formative research and programme learning

See section 3.5.3 on formative research above. As mentioned, formative research will take place in a purposive sample of health facilities and community catchment areas across the sites where iKMC interventions will be developed. The health facilities to be included as sites in the qualitative study will be selected to ensure location, representativeness of facility characteristics eligible for implementation, and other key variables. The purpose of the formative research is to contribute to a first round of formative data collection, thus pragmatic actions are planned to ensure contextual information and perspectives from different stakeholders are obtained and synthesized to be used for model development. Ongoing programme learning throughout the model optimization phase will provide additional insights to further develop and refine the model.

Participants for formative research will be identified for the different activities planned as below:

- 1) IDIs with women who had preterm birth or LBW babies who were cared for in a study facility in the last month will be identified by research assistants from the facility registry
- 2) Focus group discussions (FGDs) with women in the community including those who gave birth in the last 12 months in a study facility or at home and women family members will be identified by research assistants through community health networks.
- 3) FGDs with men in the community including partners of women those who gave birth in the last 12 months in a study facility or at home will be identified by research assistants through community health networks.
- 4) Small group (2-3 people) or individual interviews (depending on feasibility) with traditional birth attendants, women and community group leaders and other community stakeholders;— will be identified by research assistants through community health networks.
- 5) Small group (2-3 people) or individual interviews (depending on feasibility) with health workers (community health workers, midwives, nurses, doctors, obstetricians, neonatologists, paediatricians and facility management) will be identified in the different health facilities.

Maximum variation sampling will be used to encourage the recruitment and sampling to reach research participants with diverse characteristics. For example, women who had preterm or LBW babies to be interviewed should include women of different ages, geographic zones, parity and ethnicities. As data will be

analyzed in parallel with data collection, we will look for thematic data saturation and adjust the sample size as necessary (e.g., discontinuing further interviews if saturation is deemed achieved, or conducting additional interviews as needed until saturation is deemed achieved).

The research teams will facilitate contact with potentially eligible participants. Each individual will be provided with an information sheet about the study, invited to participate by the research team, and if they agree, asked to provide consent.

During the model optimization phase, the programme learning team will conduct individual or small group interviews with mothers, fathers and community members, health workers, CHWs, and other stakeholders to redesign and refine the iKMC delivery model to improve its ability reach effective and quality KMC coverage. Users' and implementers' perspective on the iKMC intervention will be explored. In total, there are seven groups of participants to consider for interview: 1) mothers who do iKMC well, 2) mothers who do iKMC but not well, 3) mothers who do not do iKMC, 4) fathers, family and community members, 5) health workers who provide iKMC in the facility, 6) CHWs who identify home births, who refer newborns born at home eligible for iKMC and/or who follow-up preterm or LBW newborns after discharge, and 7) other stakeholders. These participants will be identified through the same networks as mentioned for the formative research.

4.1.2 For the outcome evaluation in the model optimization phase and the stepped-wedge trial phase

Recruitment strategy of participants for the evaluation of the primary outcome in the model optimization phase and the stepped-wedge trial phase will be the same.

Recruitment of participants involves the following activities in the community, primary-care facility, and iKMC implementing facilities. Community-based activities aim to improve identification of eligible babies that are born outside the study facility. The primary care facilities, staff/ health workers will be oriented, sensitized and trained to identify pregnant women who are likely to give birth to a preterm or LBW baby. They will be trained to 1) refer pregnant women with risk of preterm birth or LBW babies to an iKMC implementing facility 2) measure birth weights immediately and accurately after birth and refer LBW requiring SNCU care in skinto-skin contact with mother or surrogates to the iKMC implementing facility. At the iKMC implementing facility, physicians will identify eligible mothers and babies in the labour room and operation theatre for those born in the facility; or in the emergency, OPD, SNCU or KMC ward, where babies will be referred. For babies who are referred, triaging will be done to categorize babies i) who need to be referred to a tertiary care hospital, ii) those who can be admitted to KMC ward and do not need SNCU care and iii) those who will need to be admitted in the M-SNCU. All staff in the study will receive extensive training in the WHO minimum package of care for preterm and LBW babies and iKMC. A register will be created and will have names of all preterm or LBW babies in all facilities. The research assistant will have access to this register to ensure that all eligible mothers and babies are enrolled in the study.

